6.2 Enrollment/Baseline

Enrollment/Baseline (Visit 1, Day 1)

- Obtain and document consent from participant on study consent form. Consent interview will be conducted in a private room separate from the procedure room.
- Verify inclusion/exclusion criteria.
- Randomize patient to Control or Intervention arm via sealed envelope.
- Administer pre-procedure survey which includes:
 - Demographic information and focused medical history.
 - Assessment of current distress level (0-10 scale).

- Escort patient to procedure room.
- Obtain baseline vital signs: heart rate, blood pressure, respiratory rate.
- If randomized to an intervention group, provide intervention-specific instructions.
 - For Intervention 1, patients will be instructed on how to put on and use the VR headset and how to select their preferred guided meditation.
 - For Intervention 2, patients will be provided with Pandora music station options or allowed to select their own option.

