11.2 Analysis Plans

Endpoints: All endpoints are measured pre- and post-procedure.

The primary endpoints are

1. Q13: a scale from 0-10, measuring pre-procedure patient distress, which will be treated as a numeric value in statistical analysis.
2. Q16: a scale from 0-10, measuring post-procedure patient distress, which will be treated as a numeric value in statistical analysis

The secondary endpoints are

1. Q12: a scale from 0-10, measuring patient pain scores, which will be treated as a numeric value in statistical analysis
2. Q17: a scale from 0-10, measuring post-procedure patient pain scores, which will be treated as a numeric value in statistical analysis
3. Q18, which is on a 5-level Likert scale, measuring satisfaction. This endpoint focuses on the post-procedure response and does not have a pre-procedure comparison.

Statistical Analysis: Responses to the questionnaire before and after the procedure will be reported using summary statistics such as means, standard deviations and proportions. The numeric difference between post vs. pre responses of Q13, Q16, Q12 and Q17 will be compared between Intervention 1 and Control in Phase I, and between Intervention 2 and Control in Phase II, using two-sample t-test. The post-responses of Q18 will be compared between the procedures in Phase I and Phase II using two-sided test for ordinal categorical variables.

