11.3 Sample Size Considerations

We expect to enroll 15 patients for Intervention 1 and 15 patients for Control for Phase I, and 15 patients for Intervention 2 and 15 patients for Control for Phase II. For the primary endpoint of Q13 and Q16 in each of the two phases, the numeric difference of post- vs. pre- responses will be compared between Intervention and Control arms. This sample size will achieve 82.8% power to detect an effect size of 1.1 at 5% significance level using a two-sided two-sample equal-variance t-test.

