APPENDIX B: PATIENT SURVEY

Notes: Items Q1 and Q2 are for staff use only. Study staff will enter the patient's ID number and randomized arm assignment before sharing the survey with patients. There will be no "back" button so patients will be unable to stumble upon this information accidentally. These items will be completed at the time of randomization.

Q16 includes meta text ("\${Q13/ChoiceGroup/SelectedChoices}") that will show to participants as the choice they selected as part of Q13.

Questions Q19 through Q23 will only be shown to participants in the relevant enrollment groups.

BMBA Pre- and Post-procedure Survey

Start of Block: Study ID

Q1 FOR STAFF: Enter Study ID number

Q2 Patient enrollment group

- Control
- Intervention 1
- Intervention 2

End of Block: Study ID

Start of Block: Demographics

Thank you for participating in this research study.

The following questions help us understand your experience in comparison to other patients like you. Please complete them to the best of your ability.

Q3 What is your age?

- 18-19 years old
- 20-29 years old
- 30-39 years old
- 40-49 years old
- 50-59 years old
- 60-69 years old
- 70-79 years old
- 80 years or older
- Prefer not to answer

Q4 What best describes your gender? (Select all that apply.)

- Female
- Male
- Transgender
- Non-binary / Gender variant
- Not listed (*please include if not listed*)

- Prefer not to answer

Q5 Are you of Hispanic, Latinx, or Spanish origin?

- Yes
- No
- Prefer not to answer

Q6 Please specify your race. (Select all that apply.)

- Asian
- Black or African American
- Native American
- Pacific Islander
- White
- Other (*please include if not listed*)

- Prefer not to answer

Q7 What is the highest degree or level of school you have completed?

- Some high school
- High school graduate, diploma or equivalent (GED)
- Some college
- Associate degree
- Bachelor's degree
- Master's degree
- Doctorate degree
- Other (*please include if not listed*)

- Prefer not to answer

End of Block: Demographics

Start of Block: Background Health

Q8 What diagnosis/diagnoses have required you to undergo one or more bone marrow biopsy?
(Select all that apply.)

- Aplastic Anemia
- Leukemia
- Lymphoma
- Multiple Myeloma
- Other (*please include if not listed*)

- Prefer not to answer

Q9 For what other medical conditions do you receive medical care? (Select all categories that apply.)

- Blood or Vascular conditions (for example blood clots)

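### Baseline distress (Q13) is rated after the envelope is opened and the arm entered, so the 'pre' half of the primary change score is a post-randomisation value

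*Combined protocol and SAP*

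**What the plan says.** Section 6.2 of the combined protocol and SAP sets out the day of the procedure as a sequence. After consent and the eligibility check comes "Randomize patient to Control or Intervention arm via sealed envelope". The next step begins "Administer pre-procedure survey which includes" and contains the current distress rating. Escort to the procedure room and vital signs follow, and only then "If randomized to an intervention group, provide intervention-specific instructions".

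The notes to Appendix B give the same order independently. Staff enter the study ID (Q1) and the "randomized arm assignment before sharing the survey with patients" (Q2). Of both items the notes say "These items will be completed at the time of randomization". There is no back button, so that "patients will be unable to stumble upon this information accidentally". The patient then answers Q3 to Q15, including Q12 (recalled pain at the last biopsy) and Q13 (distress today), and gives the iPad back to staff until after the procedure.

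Section 11.2 makes Q13 and Q16 the primary endpoints and states: "The numeric difference between post vs. pre responses of Q13, Q16, Q12 and Q17 will be compared between Intervention 1 and Control", with the parallel comparison for Phase II. Section 11.3 bases the sample size on the same contrast for the primary endpoint: "the numeric difference of post- vs. pre- responses will be compared between Intervention and Control arms".

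**The concern.** A change score is protected by randomisation only if allocation cannot have affected its baseline. Here Q13 is recorded after the arm is known to at least the staff member running the session. It asks about distress on the day, under an introduction that points to the procedure about to happen. A patient who has just learned that they will, or will not, get the headset or the music could reasonably answer differently.

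Such a shift would enter the primary comparison directly unless Q16 moved by the same amount. The direction cannot be predicted. Relief at being given an intervention would lower Q13 in that arm and make its later reduction look smaller. Unease about the headset would do the opposite. Adjusting for Q13 as a covariate would not repair this, because the covariate itself would have been affected by allocation. Q12, the 'pre' value for the secondary pain comparison, sits in the same survey.

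**Working it through.** **1. Is the order real?** Two separate places agree. Section 6.2 puts the envelope before the survey. Appendix B puts entry of the arm before the survey is shared and ties it to randomisation. The sequence is therefore not an accident of how the bullets in 6.2 were arranged.

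**2. Is disclosure controlled?** The missing back button protects the survey screen. Arm-specific instructions come after the survey, which suggests that patients are not meant to know their arm at Q13. No text says that the envelope result is withheld from the patient, that staff must not mention it, or that the person handing over the iPad is unaware of it.

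**3. Is the arm needed that early?** Nothing in the documents requires it. The survey's first arm-dependent display follows Q18, and escort and instructions in 6.2 come after the survey.

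**4. How would a shift propagate?** Suppose Q13 moves by *s* points in one arm and a fraction *c* of that is repeated in Q16. That arm's mean post-minus-pre change moves by *cs* − *s* = −(1 − *c*)*s*. The bias in SD units is *b* = (1 − *c*)*s* / SD.

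**5. The plan's own power figure (Section 11.3).** Inputs: 15 per arm, effect size 1.1, two-sided 5% level, equal-variance t-test.
- Degrees of freedom: 15 + 15 − 2 = 28; critical value 2.048.
- Noncentrality: 1.1 × √(15/2) = 3.012.
- Power from the noncentral t: 0.8284, which reproduces the stated 82.8%.

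**6. Illustration.** The documents give no SD, shift or carry-over, so these are assumptions: *s* = 0.5 points in one arm; SD of change 2, 2.5 or 3 points; *c* = 0, ½ or 1. The rejection rate with no true effect uses noncentrality *b*√7.5. Power against a true effect of 1.1 uses (1.1 ∓ *b*)√7.5.

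| Carry-over into Q16 | SD of change | *b* | Rejection, no true effect | Power, bias against | Power, bias in favour |
|---|---|---|---|---|---|
| Half (net 0.25 points) | 3 | 0.083 | 5.6% | 76.7% | 87.9% |
| Half | 2.5 | 0.100 | 5.8% | 75.3% | 88.7% |
| Half | 2 | 0.125 | 6.3% | 73.2% | 89.9% |
| None (net 0.5 points) | 3 | 0.167 | 7.3% | 69.4% | 91.7% |
| None | 2.5 | 0.200 | 8.3% | 66.3% | 93.0% |
| None | 2 | 0.250 | 10.1% | 61.3% | 94.6% |
| Full | any | 0 | 5.0% | 82.8% | 82.8% |

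At these SDs a true effect of 1.1 SD is 2.2 to 3.3 points. A simulation with 200,000 replicates agreed with the calculated rejection rates and with the power under adverse bias to within about 0.2 percentage points.

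**The case against.** The strongest reply is that no harm has been shown. Q13 is a fixed 0–10 item that the patient answers alone on an iPad, so staff knowledge matters only if it reaches the patient. What text there is suggests that it should not: the back button is removed, and instructions are given later, in a different room from the one used for consent. Section 13 provides staff training on how to speak to patients. The envelope procedure and the Manual of Procedures mentioned elsewhere are not in the document and may deal with disclosure. Bias needs three things together: the patient learns the arm, the rating shifts, and the shift does not carry into Q16. Q16 shows patients their own Q13 answer, which favours carry-over. The larger figures in the table need no carry-over at all. Patients know their arm at Q16 in any case, so reporting bias remains after the change. Q12 concerns a past event, so allocation could affect only its recall. A single sentence withholding the arm until the survey is returned might be enough.

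Much of this stands and limits the claim: this is an uncontrolled risk of unknown size and direction, not a demonstrated bias. It does not change the order written in 6.2 and Appendix B. The training described in Section 13 says nothing about disclosing the arm. A withholding rule is weaker, because it relies on every staff member keeping to it, whereas a baseline completed before allocation cannot be affected by allocation. That bias in Q16 is unavoidable is no reason to leave an avoidable route open in Q13.

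**Conclusion.** The concern holds. As written, the baseline for the primary endpoint, and the one for the secondary pain comparison, is recorded after randomisation by a process in which staff already know the arm, and disclosure to the patient is controlled only on the survey screen. The order is certain. Whether it causes bias is not. Under the assumed 0.5-point shift with half carried over, the false-positive rate moves only from 5% to 5.6–6.3%, but power moves by roughly 5 to 10 percentage points. With no carry-over the false-positive rate is 7.3–10.1%, and with full carry-over nothing changes. The shift, the SD and the carry-over are all assumptions. The point should be corrected because the remedy is nearly free and closes this route completely. It is not evidence that the trial's result would be wrong.

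**What to change.** In Section 6.2, move the randomisation step to after the patient has completed Q3–Q15 and returned the iPad. In Appendix B, keep Q1 at the start. Move Q2 to a staff-only page after the patient-facing divider and before the post-procedure block, still with no back button. Amend the note so that only Q2 is completed at randomisation. Both Q13 and Q12 then become true pre-randomisation values.

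The cost is one protocol amendment with IRB approval, which Section 14.2 and the Appendices statement require, and a small survey rebuild to move one item. No patients, visits or data are added, and the stated 82.8% power is unchanged. The change does not address open-label reporting bias in Q16.

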6.3 Treatment Period

Visit 1, Day 1

- Confirm patient is comfortable proceeding with assigned intervention during BMBA procedure.
- Standard of care BMBA procedure.
- Assess post-procedure vital signs: heart rate, blood pressure, respiratory rate.
- Administer post-procedure questionnaire, which includes:
 - Assessment of current distress level (0-10 scale).
 - 0-10 Numeric Pain Intensity scale.
 - Patient satisfaction questions.

6.4 Withdrawal Visit/Discontinuation of Therapy

If a participant withdraws early or terminates participation, they will be requested to complete the post-procedure questionnaire, if deemed appropriate by study staff.

7 Study Procedures and Evaluations

7.1 Study Procedures/Evaluations

- Medical History:
 - Pre-procedure questionnaire will obtain diagnosis requiring BMBA, general reasons for receiving medical care, and history of previous BMBA procedures.
- Physical examination:
 - Vital signs, including heart rate, blood pressure, and respiratory rate.

8 Evaluation of Safety

8.1 Specification of Safety Parameters

8.1.1 Unanticipated Problems

Unanticipated problems (UAPs) include, in general, any incident, experience, or outcome that meets the following criteria:

- unexpected in terms of nature, severity, or frequency given (a) the research procedures that are described in the protocol-related documents, such as the IRB-approved research protocol and informed consent document; and (b) the characteristics of the participant population being studied;

UAPs are considered to pose risk to participants or others when they suggest that the research places participants or others at a greater risk of harm (including physical, psychological, economic, or social harm) than was previously known or recognized.

8.1.2 Adverse Events

An adverse event is any untoward or unfavorable medical occurrence in a human participant, including any abnormal sign (for example, abnormal physical exam or laboratory finding), symptom, or disease, temporally associated with the participant's participation in the research, whether or not considered related to the participant's participation in the research.

Potential adverse events include fainting or lightheadedness during or post-procedure, bruising resulting from needle insertion, prolonged bleeding at biopsy site, discomfort at the site during or post-procedure, infection, dizziness, nausea, disorientation, and vertigo.

8.1.3 Serious Adverse Events

A serious adverse event (SAE) is one that meets one or more of the following criteria:

- Results in death
- Is life-threatening (places the participant at immediate risk of death from the event as it occurred)
- Is disabling or incapacitating
- Results in inpatient hospitalization or prolongation of existing hospitalization
- Results in a persistent or significant disability or incapacity
- Results in a congenital anomaly or birth defect
- An important medical event that may not result in death, be life threatening, or require hospitalization may be considered an SAE when, based upon appropriate

medical judgment, the event may jeopardize the participant or may require intervention to prevent one of the outcomes listed in this definition.

Potential SAEs include anaphylactic reaction after lidocaine or analgesic administration, post-biopsy bleeding, and severe infection.

8.2 Safety Assessment and Follow-Up

The PI will follow adverse events with start dates occurring any time after informed consent is obtained until 7 (for non-serious AEs) or 30 days (for SAEs) after the last day of study participation. Events will be followed for outcome information until resolution or stabilization.

8.3 Recording Adverse Events

The following subsections detail what information must be documented for each adverse event occurring during the time period specified in Section 8.2 Safety Assessment and Follow-Up.

8.3.1 Relationship to Study Intervention

The relationship to study intervention or study participation must be assessed and documented for all adverse events. Evaluation of relatedness must consider etiologies such as natural history of the underlying disease, concurrent illness, concomitant therapy, study-related procedures, accidents, and other external factors.

The following guidelines are used to assess relationship of an event to study intervention:

1. Related (Possible, Probable, Definite)
 - a. The event is known to occur with the study intervention.
 - b. There is a temporal relationship between the intervention and event onset.
 - c. The event abates when the intervention is discontinued.
 - d. The event reappears upon a re-challenge with the intervention.
2. Not Related (Unlikely, Not Related)
 - a. There is no temporal relationship between the intervention and event onset.
 - b. An alternate etiology has been established.

8.3.2 Expectedness

The PI is responsible for determining whether an AE is expected or unexpected. An AE will be considered unexpected if the nature, severity, or frequency of the event is not

consistent with the risk information previously described for the intervention. Risk information to assess expectedness can be obtained from published medical literature, the protocol, or the informed consent document.

8.3.3 Severity of Event

Adverse events will be graded for severity according to the Common Terminology Criteria for Adverse Events (CTCAE) version 5.0.

8.3.4 Intervention

Any intervention implemented to treat the adverse event must be documented for all adverse events.

8.4 Safety Reporting

8.4.1 Reporting to IRB

8.4.1.1 *Unanticipated Problems*

All incidents or events that meet criteria for unanticipated problems (UAPs) as defined in Section 8.1.1 Unanticipated Problems require the creation and completion of an unanticipated problem report form (OHR-20).

UAPs that pose risk to participants or others, and that are not AEs, will be submitted to the IRB on an OHR-20 form via the eazUP system within 10 working days of the investigator becoming aware of the event.

UAPs that do not pose risk to participants or others will be submitted to the IRB at the next continuing review.

8.4.1.2 *Adverse Events*

Grade 1 AEs will be reported to the IRB at continuing review.

Grade 2 AEs will be reported to the IRB at the time of continuing review.

8.4.1.3 *Serious Adverse Events*

SAEs will be reported to the IRB on OHR-10 forms via the electronic reporting system (eSAEY) according to the required time frames described below.

Grade 3-4 AEs that are unexpected and deemed to be at least possibly related to the study will be reported to the IRB within 2 working days of knowledge of the event.

Grade 3-4 AEs that are deemed unrelated to the study will be reported to the IRB within 5 working days.

Grade 5 AEs will be reported to the IRB within one working day of knowledge of the event.

All SAEs will be submitted to the IRB at continuing review, including those that were reported previously.

8.4.2 Reporting to SKCC DSMC

All AEs and SAEs, safety and toxicity data, and any corrective actions will be submitted to the DSMC per the frequency described in the SKCC DSMP. The report to the SKCC DSMC will also include any unanticipated problems that in the opinion of the PI should be reported to the DSMC.

For expedited reporting requirements, see table below:

DSMC AE/SAE Reporting Requirements

| | Grade 1 | Grade 2 | | Grade 3 | | | | Grades 4 and 5 |
|----------------------------------|--|--|--|-------------------------------|--|-------------------------------|--|--|
| | Unexpected and Expected | Unexpected | Expected | Unexpected | | Expected | | Unexpected and Expected |
| | | | | With Hospitalization | Without Hospitalization | With Hospitalization | Without Hospitalization | |
| Unrelated Unlikely | Reviewed at Quarterly DSMC Meeting and IRB Annual Review | Reviewed at Quarterly DSMC Meeting and IRB Annual Review | Reviewed at Quarterly DSMC Meeting and IRB Annual Review | 5 Working Days | Reviewed at Quarterly DSMC Meeting and IRB Annual Review | 5 Working Days | Reviewed at Quarterly DSMC Meeting and IRB Annual Review | Phase I - 48 Hours (Death: 24 Hours) Phase II - 5 working days |
| Possible Probably Definite | Reviewed at Quarterly DSMC Meeting and IRB Annual Review | Reviewed at Quarterly DSMC Meeting and IRB Annual Review | Reviewed at Quarterly DSMC Meeting and IRB Annual Review | 48 Hours (Death: 24 Hours) | Phase I - 48 Hours | 48 Hours (Death: 24 Hours) | Reviewed at Quarterly DSMC Meeting and IRB Annual Review | Phase I and Phase II - 48 Hours (Death: 24 Hours) |

8.4.3 Reporting to Funding Sponsor

Funding provided by the DAISY Foundation requires an interim report after patient enrollment is complete, anticipated as 6 months after start date. A final report of findings is due after data analysis is complete, no later than 1 year after the study start date.

8.4.4 Reporting of Pregnancy

Pregnant women are not commonly a part of the BMBA patient population, and no participants will undergo pregnancy tests. As the study takes place for a single day, no ongoing reporting for pregnancy will be required.

8.5 Halting Rules

Six or more patients experiencing Grade 4 and 5 AEs, as well as three or more patients experiencing SAEs, will prompt a temporary suspension of enrollment until a safety review can be convened.

9 Study Oversight

In addition to the PI's responsibility for oversight, study oversight will be under the direction of the SKCC's Data and Safety Monitoring Committee (DSMC). The SKCC DSMC operates in compliance with a Data and Safety Monitoring Plan (DSMP) that is approved by the NCI.

10 Clinical Site Monitoring and Auditing

Clinical site monitoring and auditing is conducted to ensure that the rights of human participants are protected, that the study is implemented in accordance with the protocol and/or other operating procedures, and that the quality and integrity of study data and data collection methods are maintained. Monitoring and auditing for this study will be performed in accordance with the SKCC's Data and Safety Monitoring Plan (DSMP) developed by the SKCC Data and Safety Monitoring Committee (DSMC). The DSMP specifies the frequency of monitoring, monitoring procedures, the level of clinical site monitoring activities (e.g., the percentage of participant data to be reviewed), and the distribution of monitoring reports. Some monitoring activities may be performed remotely, while others will take place at the study site(s). Appropriate staff will conduct monitoring activities and provide reports of the findings and associated action items in accordance with the details described in the SKCC DSMP.

11 Statistical Considerations

